### 2.3.2. Benefit Assessment

No clinical benefit is expected for the healthy participants who are to be enrolled into this study.

This open-label, single dose PK study in healthy Chinese participants will provide initial pharmacokinetic, safety, tolerability and immunogenicity data in Chinese population, to evaluate the ethnic sensitivity in Chinese population versus overseas population.

Participants enrolled into this study are Chinese healthy participants. The participants' involvement will contribute to the understanding of the PK and safety profiles of GSK3511294 100mg and 300 mg administered SC in the Chinese population.

### 2.3.3. Overall Benefit: Risk Conclusion

Although no clinical benefit is expected for recruited participants, overall the benefit:risk balance for this PK study to be performed in 20 healthy participants is considered acceptable based on available data from FTIH study and risk mitigation strategy implemented for this protocol. The study provides the opportunity to generate PK, safety and tolerability information in Chinese population, thereby supporting subsequent dose justification for GSK3511294 in Chinese patients.

Taking into account the measures taken to minimize risk to participants participating in this study, the potential risks identified in association with are justified by the anticipated benefits that may be afforded to healthy participants.

## 3. OBJECTIVES AND ENDPOINTS

Objectives	Endpoints
Primary	

 
To evaluate the plasma pharmacokinetics of single subcutaneous doses of GSK3511294 in Chinese healthy participants
 
	
 
Plasma pharmacokinetic parameters of GSK3511294 after a single subcutaneous dose: AUC(0-∞), AUC(0-t), AUC(0-Week4), AUC(0-Week12), AUC(0-Week26), %AUCex, Cmax, tmax, tlast, CL/F, Vz/F, λz and t½ when assessable*
 

Secondary	

 
To assess the safety and tolerability of single subcutaneous (SC) doses of
 
	
 
Incidence of adverse events (AE), serious adverse events (SAE)
 

Objectives	Endpoints

GSK3511294 in Chinese healthy participants
 
 
To assess the immunogenicity of GSK3511294 in Chinese healthy participants
 
	
 
Change from baseline in laboratory safety data, at each post-dose timepoint during the 26 week treatment period, which including hematology and clinical chemistry
 
Absolute values of C3 & C4 at each timepoint and the ratio to baseline at each post-dose timepoint during the 26 week treatment period
 
Change from baseline in vital signs, at each post-dose timepoint during the 26 week treatment period, which including blood pressure, body temperature and pulse rate
 
Change from baseline in Electrocardiograms (ECG), at each post-dose timepoint during the 26 week treatment period
 
Frequency and titres of binding anti-drug antibodies (ADAs) to GSK3511294, before and after GSK3511294 administration.
 

\* PK parameter abbreviations: AUC(0-∞) = area under the concentration-time curve from time zero (pre-dose) extrapolated to infinite time; AUC(0-t) = area under the concentration-time curve from time zero (pre-dose) to last time of quantifiable concentration within a participant across all treatments; AUC(0-WeekN) = area under the concentration-time curve from time zero to WeekN; %AUCex = percentage of AUC(0-∞) obtained by extrapolation; Cmax = maximum observed concentration; tmax=time of occurrence of Cmax; tlast = time of last quantifiable concentration; CL/F = apparent clearance following subcutaneous dosing; Vz/F = apparent volume of distribution after subcutaneous administration; λz= terminal elimination rate constant; t1/2 = terminal phase half-life.

The definition of applicable intercurrent events and corresponding strategy will be presented in Reporting and Analysis Plan (RAP).

## **4. STUDY DESIGN**

### **4.1. Overall Design**

This is a single-centre, single dose, open-label study to evaluate the pharmacokinetics, safety, tolerability and immunogenicity of subcutaneously administered GSK3511294 100 mg and 300 mg in Chinese healthy participants.

### **4.2. Scientific Rationale for Study Design**

All participants will receive a single dose of GSK3511294 subcutaneously of either 100 mg or 300 mg.

The 100 mg cohort (10 participants) will be initiated first.

The study team will review the safety data from the 10 participants in the 100 mg cohort before initiating 300mg cohort: at least 4-week safety data. In case of safety concerns, further investigation of the safety concerns will be conducted (including reviewing PK data if deemed necessary) before initiating the 300 mg cohort. Criteria for Temporarily Delaying the start of the 300 mg cohort have been listed in Section 5.5.

#### **Screening period (2 weeks):**

All participants will attend the unit for screening within 14 days prior to their dosing date.

#### **Study period (26 weeks)**

Participants will be admitted the day before dosing, and all participants will remain in the CRU for approximately 8 hours after dosing for safety observation and other procedures. In the event of an acute severe reaction (e.g., anaphylaxis) following administration of study intervention, there are personnel/staff onsite at the treatment facility who are appropriately trained in basic life support to manage the participant including administration of medications (e.g., epinephrine), and have access to a system that can promptly transport the participant to another facility for additional care if appropriate. Participants will be discharged only if the Investigator deems it safe for the participant to leave the unit.

Participants will return CRU for regular out-patient visits throughout the study according to Schedule of Activities.

To assess the potential exposure in Chinese subjects simulations were performed based on data from the FTIH study. Based on the assumption that body weight is the only impact factor on pharmacokinetics profile of GSK3511294, compared with a typical Caucasian subject of 70 kg, exposure in a typical Chinese subject of 60 kg for up to 183 days will cover 96% of overall exposure ( $AUC_{0-183d}/AUC_{0-\infty}$ ) for both 100 mg and 300 mg cohort. Even in the extreme case when a typical Chinese subject's clearance is only half of a Caucasian's, the exposure within 183 days will still cover 83% of overall exposure for both cohorts. In both cases, the coverage of exposure makes the

extrapolation of AUC valid. Hence, a study period of 26 weeks is deemed sufficient for assessing pharmacokinetics profile of GSK3511294 in Chinese.

**Additional AE Follow up period (4 weeks):**

All participants will be telephoned as the additional AE follow up visit at Week 30 by investigators to further collect the safety information.

**Total duration:** The scheduled maximum study duration for each participant will be up to 32 weeks including up to 2 weeks screening period and 4 weeks AE follow up period.

**Data Monitoring/ Other Committee:** No

### **4.3. Participant Input into Design**

Not applicable.

### **4.4. Justification for Dose**

GSK3511294 was investigated in a FTIH study (205722) outside of China over the dose range 2-300 mg SC. GSK3511294 was well tolerated up to a single SC dose of 300 mg and expected extended PK and pharmacology were demonstrated. Also, GSK3511294 is an antagonist of IL-5 that belongs to the same class as mepolizumab. Based on the pharmacology results of study 205722 and prior knowledge of mepolizumab pharmacology a dose of 100 mg SC administered every 26 weeks has been selected for investigation in the global Phase 3 clinical development program for severe asthma with an eosinophilic phenotype that is planning to enrol Chinese patients. Therefore a single SC dose of GSK3511294 100 mg is proposed to be investigated in this study to assess the PK and safety of GSK3511294 in the Chinese population. In addition a single SC dose of 300 mg is also proposed to be investigated in this study to provide further safety data above the 100 mg SC dose (the dose selected for the global Phase 3 clinical development program for severe asthma with an eosinophilic phenotype) CCI

In study 205722 conducted in participants with mild/moderate asthma, overall linear PK was observed over the SC dose range 10 to 300 mg of GSK3511294, without evidence of target mediated disposition. This suggests that any difference in PK between Chinese and overseas populations due to the variability of target expression is considered unlikely. Slight difference in exposure between Chinese and overseas populations is possible, as body weight is a determinant of GSK3511294 exposure, similar to other mAbs. Approximately 12% higher exposure (AUC) is anticipated in Chinese participants compared with overseas participants given 100 mg and 300 mg fixed doses, considering 60 kg vs. 70 kg as the typical body weight in Chinese and overseas populations. In FTIH study 205722, GSK3511294 was well tolerated in patients with mild/moderate asthma receiving single SC doses up to 300 mg. The exposure (AUC) observed at 300 mg SC was 25-fold lower than the monkey exposure observed at the 100 mg /kg NOAEL dose, which supports the selection of a SC dose of 100 mg and 300 mg GSK3511294 for investigation in Chinese participants in this study. Furthermore, as an IgG1 monoclonal antibody, the elimination of GSK3511294 is via intracellular catabolism (proteolysis).

This clearance mechanism is non-specific and has large capacity. Reports of inter-ethnic differences in the non-specific pathways of protein elimination have not been identified and inter-ethnic differences in the catabolism of GSK3511294 are not anticipated, as was shown with mepolizumab.

In summary, GSK3511294 single SC doses of 100 mg and 300 mg are considered appropriate doses for investigation of the PK, tolerability and safety of GSK3511294 in Chinese healthy participants in this study in support of dose justification for Chinese patients with severe asthma with an eosinophilic phenotype [REDACTED]

#### **4.5. End of Study Definition**

The end of the study is defined as the date of the last visit of the last participant in the study.

A participant is considered to have completed the study if he/she has completed all phases of the study including the exit visit at week 26.

### **5. STUDY POPULATION**

Prospective approval of protocol deviations to recruitment and enrollment criteria, also known as protocol waivers or exemptions, is not permitted.

#### **5.1. Inclusion Criteria**

Participants are eligible to be included in the study only if all of the following criteria apply:

##### **1. Age**

Participant must be 18 to 45 years of age inclusive, at the time of signing the informed consent.

##### **2. Type of Participant**

Participants who are overtly healthy. Healthy is defined as being free from clinically significant illness or disease as determined by a responsible and experienced physician, based on a medical evaluation including medical history, physical examination, vital sign, laboratory tests, chest X-ray and ECG. A subject with a clinical abnormality or laboratory parameter(s) which is/are not specifically listed in the inclusion or exclusion criteria, outside the reference range for the population being studied, may be included only if the investigator (in consultation with the GSK medical monitor if necessary) agree and document that the finding is unlikely to introduce additional risk factors and will not interfere with the study procedures. Chinese are defined as having four ethnic Chinese grandparents, holding a Chinese Identification card and being able to speak Chinese.

### 3. Weight

Body weight  $\geq 50.0$ kg for males,  $\geq 45.0$ kg for females, and body mass index (BMI) within the range [19.0 – 26.0] kg/m^2 (inclusive).

### 4. Sex and Contraceptive/Barrier Requirements

Male and female participants.

Contraceptive use by men and/or women should be consistent with local regulations regarding the methods of contraception for those participating in clinical studies.

- a. Male Participants: as GSK3511294 is a monoclonal antibody that is not anticipated to interact directly with Deoxyribonucleic acid (DNA) or other chromosomal material with minimal exposure through semen expected, male participants will not be required to use contraception during the study, nor are they prohibited from donating sperm.
- b. Female Participants: a female participant is eligible to participate if she is not pregnant (see [Appendix 4](#)), not breastfeeding, and not a woman of childbearing potential as defined in [Appendix 4](#).

### 5. Informed Consent

Capable of giving signed informed consent as described in Section [10.1](#) which includes compliance with the requirements and restrictions listed in the informed consent form (ICF) and in this protocol.

#### 5.2. Exclusion Criteria

Participants are excluded from the study if any of the following criteria apply:

##### Medical Conditions

1. History or presence of/significant history of or current cardiovascular, respiratory, hepatic, renal, gastrointestinal, endocrine, hematological, or neurological disorders capable of significantly altering the absorption, metabolism, or elimination of drugs; constituting a risk when taking the study intervention or interfering with the interpretation of data
2. Hypersensitivity: participants with allergy/intolerance to a monoclonal antibody or biologic. Or participants with a previous history of clinically significant multiple or severe drug allergies, intolerance to topical corticosteroids, or severe post-treatment hypersensitivity reactions (including, but not limited to, erythema multiforme major, linear immunoglobulin A (IgA) dermatosis, toxic epidermal necrolysis, and exfoliative dermatitis).
3. Latent or chronic infections (e.g., genital herpes, urinary tract infections) or at risk if infection. Or opportunistic infection within 6 months prior to screening (e.g., a non-tuberculous mycobacterial infection or cytomegalovirus, pneumocystosis, aspergillosis).

4. Parasitic infection: Participants with a known, pre-existing parasitic infestation within 6 months prior to Screening.
5. Vasculitis: Participants with current diagnosis of vasculitis. Participants with high clinical suspicion of vasculitis at screening will be evaluated and current vasculitis must be excluded prior to enrolment.
6. Alcohol/Substance Abuse: A history (or suspected history) of alcohol misuse or substance abuse
7. COVID-19:
  - a-Participants with signs and symptoms suggestive of COVID-19 (i.e. fever, cough, etc) within 14 days of inpatient admission.
  - b- Participants with known COVID-19 positive contacts in the past 14 days

#### **Prior/Concomitant Medication**

8. Use of prescription or non-prescription drugs, including vaccines, vitamins, herbal and dietary supplements within 7 days (or 14 days if the drug is a potential enzyme inducer) or 5 half-lives (whichever is longer) prior to the first dose of study medication, unless in the opinion of the Investigator and GSK Medical Monitor the medication will not interfere with the study procedures or compromise subject safety.

Note: Any approved COVID-19 vaccine by local government is permitted, but it should avoid being administered within 14 days of GSK3511294. If the vaccination within 14 days is unavoidable, then alternative time interval can be considered on a case by case basis in conjunction with the medical monitor. Experimental COVID-19 vaccines are not permitted.

#### **Prior/Concurrent Clinical Study Experience**

9. The participant had participated in a clinical study or post-marketing study with an investigational or a non-investigational product during the previous 4 months or 5 half-lives (whichever is longer) preceding the administration of study medication of this study.
10. Exposure to more than 4 new chemical entities within 12 months prior to the dosing day.
11. The participant plans to concurrently participate in another clinical study or post-marketing study. Or have a treatment with biologic agents (such as monoclonal antibodies including marketed drugs) within 3 months or 5 half-lives (whichever is longer) prior to dosing
12. Participation in the study would result in loss of blood or blood products in excess of 500 mL within a 56 day period.

#### **Diagnostic assessments**

13. ALT>1.5x ULN

14. Total bilirubin >1.5x ULN (isolated bilirubin >1.5x ULN is acceptable if bilirubin is fractionated and direct bilirubin <35%).
15. QTcF >450 msec.

Notes:

- The QTc is the QT interval corrected for heart rate, for the purposes of standardisation, QTc corrected by Fridericia's formula (QTcF) will be used across sites with central over-read to limit variability.
  - For purposes of data analysis, QTcF will be used as specified in RAP.
16. Abnormal chest X-Ray: A chest X-ray or CT scan that reveals evidence of clinically significant abnormalities. A chest X-ray must be taken at screen visit if a chest X-ray or CT scan is not available within 6 months prior to screen visit.  
  
Note: Participants should not be enrolled if the chest x-ray used in this study would cause exposure to ionising radiation in excess of 10 mSv above background over the previous three year period as a result of occupational exposure or previous participation in research studies (Clinically justified therapeutic or diagnostic exposures are not included in this cumulative calculation).
  17. Presence of hepatitis B surface antigen (HBsAg), positive hepatitis C antibody test result at screen or within 3 months prior to dose
  18. A positive pre-study drug/alcohol screen
  19. A positive test for HIV antibody.
  20. A positive test for Parasite screening.
  21. A positive test for COVID-19 at screening or during the period between screening and dosing of study drug.

### **5.3. Lifestyle Considerations**

#### **5.3.1. Meals and Dietary Restrictions**

- Participants should fast for at least 8 hours before the screening visit and will be allowed to eat during the screening visit after blood draw for clinical chemistry has been completed. For other visits, fasting is not required.
- Participants will abstain from alcohol for 24 hours before the start of dosing period

#### **5.3.2. Activity**

- Participants will abstain from strenuous exercise for 48 hours before each blood collection for clinical laboratory tests.

## 5.4. Screen Failures

Screen failures are defined as participants who consent to participate in the clinical study but are not subsequently entered in the study. A minimal set of screen failure information is required to ensure transparent reporting of screen failure participants to meet the Consolidated Standards of Reporting Trials (CONSORT) publishing requirements and to respond to queries from regulatory authorities. Minimal information includes demography, screen failure details, eligibility criteria, any protocol deviations and any serious adverse events (SAEs).

Individuals who do not meet the criteria for participation in this study (screen failure) may not be rescreened.

## 5.5. Criteria for temporarily delaying initiation of the 300 mg cohort

If one or more of the following criteria are met, initiation of the 300 mg cohort will be temporarily delayed and all available safety data will be reviewed by the sponsor and investigator(s):

- one or more participants has:
  - a Serious Adverse Event (SAE) that is considered by the investigator to be possibly related to study drug
  - an episode of acute renal failure requiring renal replacement therapy that is at least possibly related to study drug
  - an episode of anaphylaxis that is considered by the investigator to be possibly related to study drug
  - an episode of angioedema that is considered by the investigator to be possibly related to study drug
  - a biopsy showing features of immune complex disease
  - 2 or more participants have severe Adverse Event (AEs) that is considered by the investigator to be possibly related to study drug

Participants who have been dosed before the time of the study delay will continue follow up visit in the study, as planned. Further participants may be dosed only if, after review, the sponsor and investigators consider it safe to do so.

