### Treatment Arms and Duration:

All participants will receive a single dose of GSK3511294 subcutaneously of either 100 mg or 300 mg.

The 100 mg cohort (10 participants) will be initiated first.

The study team will review the safety data from the 10 participants in the 100 mg cohort before initiating 300mg cohort: at least 4-week safety data. In case of safety concerns, further investigation of the safety concerns will be conducted (including reviewing PK

data if deemed necessary) before initiating the 300 mg cohort. Criteria for Temporarily Delaying the start of the 300 mg cohort have been listed in Section 5.5.

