#### **6.6. Dose Modification**

There are no specific adjustment/stopping criteria for this study. Each participant will receive a single dose of GSK3511294 100mg or 300 mg subcutaneously in this study.

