		Packaging and Labelling	Study Intervention will be provided in PFS. Each PFS will be labelled as required per country requirement.
PFS=Pre-filled safety syringe, IMP=Investigational Medicinal Product			
		
There are no specific adjustment/stopping criteria for this study. Each participant will receive a single dose of GSK3511294 100mg or 300 mg subcutaneously in this study.	
Study intervention Assignment	
This is an open-label, single dose, non-randomized study.		
Interim Analysis	
No formal interim analysis is planned for this study.The 100mg cohort (10 participants) will be initiated first. The study team will review the safety data from the 10 participants in the 100mg cohort before initiating 300mg cohort: at least 4-week safety data. In case of safety concerns, further investigation of the safety concerns will be conducted (including reviewing PK data if deemed necessary) before initiating the 300 mg cohort. Criteria for Temporarily Delaying the start of the 300 mg cohort described in Section 5.5 of the Protocol.		

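### Protocol 5.5 names only a delay in starting the 300 mg cohort, so a dosing hold is not clearly required for other undosed participants when a listed event occurs

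*Protocol*

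**What the plan says.** Section 5.5 of the protocol is headed as criteria for delaying the start of the 300 mg cohort. Its trigger sentence reads: "If one or more of the following criteria are met, initiation of the 300 mg cohort will be temporarily delayed". The same sentence requires the sponsor and investigators to review the safety data. The list covers possibly related serious adverse events, anaphylaxis and angioedema, renal failure needing replacement therapy, biopsy features of immune complex disease, and severe related events in two or more participants. It does not say in which cohort the event must occur.

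The section closes with two sentences: "Participants who have been dosed before the time of the study delay will continue follow up visit in the study, as planned" and "Further participants may be dosed only if, after review, the sponsor and investigators consider it safe to do so".

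The synopsis (1.1) points to the section in these words: "Criteria for Temporarily Delaying the start of the 300 mg cohort have been listed in Section 5.5". Section 4.2 does the same, and SAP 1.2 refers to "Criteria for Temporarily Delaying the start of the 300 mg cohort described in Section 5.5 of the Protocol". Section 4.2 also sets the review of the 10 participants at 100 mg: "before initiating 300mg cohort: at least 4-week safety data". Section 6.6 states: "There are no specific adjustment/stopping criteria for this study". SAP 1.2 repeats that statement.

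**The concern.** The list of events is open as to cohort and time, but the named action fits only one moment, before the first 300 mg dose. Once that dose is given, there is no initiation left to delay. While the 100 mg cohort is still being dosed, delaying the 300 mg start does not of itself stop the next 100 mg dose.

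If a listed event occurs at either of those times, the sponsor and the investigator could read 5.5 as requiring a hold or as not applying. They would have to settle that while the event is unfolding. The participants are healthy and no clinical benefit is expected for them (2.3.2). Earlier experience at 300 mg is 6 participants, all with mild or moderate asthma (6.8).

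**Working it through.** No figure in the plan bears on this point. The check is a reading of the text in each situation, then a count.

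**Step 1. What 5.5 requires, by timing of the event**

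| Listed event occurs | Named action: delay 300 mg initiation | Closing sentence of 5.5 | Hold clearly required? |
|---|---|---|---|
| During 100 mg dosing | Can be taken, but stops no 100 mg dose | Can be read to hold the remaining 100 mg doses | No, for the 100 mg participants |
| After 100 mg dosing, before the first 300 mg dose | Can be taken, and holds the whole 300 mg cohort | Agrees with the named action | Yes, for the 300 mg cohort |
| After the first 300 mg dose | Nothing left to delay | Can be read to hold the remaining 300 mg doses | No |
| While additional recruits are being dosed | Does not mention them | Can be read to hold them | No |

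**Step 2. Can the closing sentence carry the wider rule?** It is restrictive and names no cohort, which favours a wider hold. However, it follows a sentence about participants dosed before the study delay, and the only delay that 5.5 defines is of 300 mg initiation. Read in sequence, it may say no more than how that delay is lifted. The heading and the three pointers favour the narrower reading.

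**Step 3. Does another section supply the hold?**

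- 7.1 gives no criteria for discontinuing study intervention.
- 9.2.1 sets no separate safety condition for additional recruits.
- 8.3.1 requires serious adverse events to reach the sponsor within 24 hours.
- 2.3.1 provides daily monitoring of serious events and regular review by a safety team.
- 8 asks that immediate concerns be discussed with the sponsor at once.
- 10.1.8 allows the sponsor to terminate the study at its discretion.
- 10.1.1 lets changes needed to remove an immediate hazard proceed without prior approval.

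These provide information and authority to act. None says that a listed event suspends dosing.

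**Step 4. Count.** Inputs: 10 planned per cohort (1.1); at most 6 additional recruits per cohort, if fewer than 6 participants have at least 18 weeks of PK data (9.2.1); no stated interval between participants.

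- Undosed after the first dose in a cohort, if dosed one at a time: 10 − 1 = 9.
- Undosed if all ten are dosed on one day: 10 − 10 = 0.
- Range: 0 to 9 of the 10 planned in a cohort.
- Additional recruits: 0 to 6 per cohort. With 10 enrolled, recruitment is triggered only when at most 5 have the data, that is, when at least 10 − 5 = 5 lack them.

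The documents give no rate for the listed events, so none is assumed.

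**The case against.** The strongest reply is that 5.5 already supplies the hold. The triggers are not limited to a cohort, the closing paragraph speaks of a study delay rather than a cohort delay, and "Further participants may be dosed only if, after review, the sponsor and investigators consider it safe to do so" is a plain restriction. To continue dosing after a related anaphylaxis, the investigator would have to disregard that sentence. The study is also single-centre and open-label, so the people who would decide are those who receive the event reports. Section 4.4 adds that 300 mg was well tolerated in the first-in-human study, and that exposure there was 25-fold below monkey exposure at the no-adverse-effect dose.

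Much of this stands. It shows that a hold is a reasonable reading and that oversight exists. It does not make the hold explicit, because the heading, the trigger sentence and every pointer say something narrower.

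Three stronger inferences are tempting, and the documents do not support them:

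- **That nothing restricts dosing after 300 mg starts.** The closing sentence and the sponsor's power to terminate contradict this.
- **That 6.6 disclaims any stopping rule for the study.** It sits under dose modification and is followed by a statement that each participant receives a single dose. Section 7.4.1 uses stopping criteria in the same individual sense. The wording is loose, but in context it is about individual dosing.
- **That the number at risk is the sum of all the maxima.** Adding 9 planned participants to 6 extra recruits in each cohort gives 21 of 32. That needs one-at-a-time dosing, an event straight after the first 300 mg dose, a PK shortfall in both cohorts, and all 12 recruits dosed later. Nor do the weeks of adverse event follow-up after the 300 mg start measure the gap, which matters only while someone remains undosed.

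**Conclusion.** The point holds as an ambiguity in a pre-specified safety rule. Section 5.5 clearly requires a hold in one situation, before the 300 mg cohort starts, and for that cohort only. For participants still undosed during 100 mg dosing, after 300 mg dosing has begun, or among additional recruits, a hold is supported by the closing sentence but not clearly required.

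The size is 0 to 9 of the 10 planned in a cohort, plus any additional recruits. It depends on a dosing interval that the documents do not state. If each cohort is dosed in a single day and no one is added, no one is affected. No analysis or reported figure changes. This is a cheap improvement for participant safety.

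**What to change.** Retitle Section 5.5 *Criteria for temporarily suspending dosing*, and replace the trigger sentence with wording such as:

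*When any criterion below is met in either cohort, dosing of everyone not yet dosed (including initiation or continuation of the 300 mg cohort and any additional recruits under Section 9.2.1) is suspended until the sponsor and investigators have reviewed all safety data to date and documented that it is safe to proceed.*

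Keep the list of events and the reviewers. In the closing paragraph, change the reference to a study delay to a suspension. Align the pointers in Protocol 1.1 and 4.2 and SAP 1.2. Optionally, begin the statement on stopping criteria in 6.6 and SAP 1.2 with *Other than the dosing suspension in Section 5.5*.

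No change to Section 5.4 is needed. Its bar on rescreening concerns people who do not meet the criteria for participation, and a lapse of the 14-day screening window can already arise under the existing delay.

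The cost is a wording amendment, with ethics committee approval and, if it is judged substantial, health authority approval (10.1.1), plus a matching edit to the SAP. Dosing might pause after a listed event, as 5.5 already accepts before the 300 mg start. No committee, visit or sample is added.
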